For data collection, the following instrument VAS Scale will be used. This scale will be applied at the beginning of the data collection. In sequence, the participants will perform the Thermography protocol, which comprises capturing images in various postures in the orthostatic position.

Afterwards, the participants will remain in the supine dorsal position on a stretcher at rest for 10 minutes to start the SNA analysis with the Ryodoraku (device that measures the electroconductivity of certain points on the skin) by the digital reading of the 24 points called ryodos (SCILIPOTI, 2007).

Continuing the procedure, immediately after the placement of the Polar V800, an instrument for analyzing heart rate variability, the placing of needles at the points carefully selected for this research begins. The needling will proceed for the experimental group using specific Traditional Chinese Acupuncture points: E36, BP6, F3, IG4, for 20 minutes while the control group will receive needling in sham points (points not recognized as Acupuncture points), with the duration of 20 minutes. Final phase, new reading with Ryodoraku and Thermography.

Ryodoraku

Based on the Ryodoraku (meridian) theory, developed by [name] (Nakatani, 1956), there are 12 meridians on the right and left side of the human body respectively. The property of Ryodoraku can reflect the condition of certain organ(s) by analyzing and comparing their mutual relations and changes with micro-electrical current. The electrical state of the acupuncture points of the human subject is measured by a computerized testing instrument with a very low electrical current. From the traditional theory, Ryodoraku is a pathological phenomenon. The mechanism can be explained by the viscera-skin sympathetic nerve reflex. The impulses from the viscera radiate to the spinal cord. The reflex zones are then reflected onto the skin surface via the efferent sympathetic nerves and appear as a longitudinal connecting system, just like meridian lines (Weng et al., 2004).

Electrodermal screening measures either skin impedance or conductance at acupuncture points as diagnostic aids for planning treatment strategies. Skin impedance is the skin's opposition to the flow of current. The practice of measuring skin impedance is based on the widely held assumption that acupuncture points are loci of decreased impedance compared to skin sites where there are no known acupuncture points (Pearson et al., 2007).

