With the aid of thermometry infrared electromagnetic waves of $0.7\text{--}1000\text{ M}$ (which the human eye is unable to identify) can be visualized, healthy human bodies emit waves with a length of $3\text{--}10\text{ M}$. Temperature differences as low as $0.1\text{ }^{\circ}\text{C}$ can be pursued and may help track response to acupuncture as opposed to needling of non-acupoints to objectively estimate effects of needling (Agarwal-Kozlowski, Lange e Beck, 2009).

Lastly, changes in temperature detected will be related to changes in blood flow when the external environment is stable (no changes in irradiative, conductive, or convective heat transfer), and thus sensitive to acute changes in sympathetic activity which would induce vasoconstriction as the vasculature is not parasympathetically innervated. This temperature rise under extreme stimuli may be due to increases in cardiac output, which may increase perfusion pressure or the release of local factors such as nitric oxide from nearby endothelial cells, and it may be sympathetically mediated but could relate to parasympathetic withdrawal that induces cardiac acceleration, suggesting a complex interplay of autonomic control (Huggins e Rakobowchuk, 2019).

Analysis of Heart Rate Variability

After the initial evaluation, the capture strap will be placed on the volunteers' chests, and the heart rate receiver (V800, Polar) will be placed on their wrists, previously validated equipment for capturing the heart rate, beat by beat, and the use of their data for HRV analysis (GAMELIN et al., 2006; KINGSLEY et al., 2005).

After placing the strap and the monitor, the individuals will be positioned in a sitting position and will remain at rest, breathing spontaneously for 20 minutes. Following that, the analysis will be made during the performance of Acupuncture.

or analysis of HRV data in the sitting position, 1000 consecutive RR intervals will be used, and during the tasks, 256 consecutive intervals will be used. Then, a manual filtering will be performed through the *Microsoft Excel* program, to eliminate premature ectopic beats and artifacts, and there will be no substitution, only the elimination of artifacts. After manual filtering, the first 1000 beating intervals are chosen and only series with more than 95% of sinus beats will be included in the study (GODOY et al., 2005). The software used to assess HRV will be the Kubios HRV.

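### Taking the first 1000 intervals of the seated rest, with no settling period set aside, risks inflating resting SDNN and SD2 and so distorting their rest-to-needling change

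*Protocol*

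**What the plan says.** Under Analysis of Heart Rate Variability (Protocol, section 2.3), the strap and monitor are fitted, and then "the individuals will be positioned in a sitting position and will remain at rest, breathing spontaneously for 20 minutes". Recording continues during acupuncture. For "analysis of HRV data in the sitting position, 1000 consecutive RR intervals will be used"; "during the tasks, 256 consecutive intervals will be used". Artefacts are deleted without substitution, and once that filtering is done "the first 1000 beating intervals are chosen". The only acceptance rule for a series is more than 95% sinus beats. The section gives no recording start time, no settling interval and no stationarity criterion, and it does not say which 256 needling intervals are taken.

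The Intervention text in the same section, repeated in Table 2, gives another sequence: thermography while standing, then "the participants will remain in the supine dorsal position on a stretcher at rest for 10 minutes", then Ryodoraku, then needling directly after the monitor is placed. It contains no seated rest.

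The Introduction makes autonomic behaviour before, during and after therapy an objective. The Primary Outcome concerns autonomic change after active and after sham acupuncture.

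**The concern.** On the natural reading, the rest recording begins as the participant moves to sitting, after lying supine. Beats during which heart rate is still adjusting to the new posture would then fall inside the analysed baseline, while the minutes closest to needling are dropped. A slow trend within a segment adds to its overall standard deviation. Resting SDNN and SD2 would be too large and SD1/SD2 too small, so SDNN and SD2 would appear to fall, and SD1/SD2 to rise, on needling for reasons unrelated to acupuncture. The Introduction treats higher variability as the healthier state, so an inflated resting SDNN could mask a true gain. What is at stake is the before-during comparison in these indices.

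**Working it through.** The plan has no figure of its own to reproduce here. The check has five steps.

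**Inputs.** From the Protocol: 20 minutes of seated rest, first 1000 intervals at rest, 256 during needling. Assumed, because the Protocol gives none of them: heart rate 60 to 80 bpm; mean RR lengthening by D = 30 to 80 ms after sitting, with time constant τ = 2 to 4 minutes; SDNN of 40 ms without the trend.

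**1. Time covered.** Minutes used = 1000/HR; minutes unused = 20 − 1000/HR.

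| HR (bpm) | Beats in 20 min | Minutes used | Minutes unused |
|---|---|---|---|
| 50 | 1000 | 20.0 | 0 |
| 60 | 1200 | 16.7 | 3.3 |
| 70 | 1400 | 14.3 | 5.7 |
| 80 | 1600 | 12.5 | 7.5 |

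The last 1000 beats therefore need no longer recording. At 50 bpm the two windows coincide. At 70 bpm they share 2000 − 1400 = 600 beats.

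**2. Inflation of SDNN.** Trend: −D·exp(−t/τ). Inflated SDNN = √(40² + s²), where s is the SD of the trend within the window. At 70 bpm:

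| D (ms), τ (min) | s, first 1000 | Inflation | s, last 1000 | Inflation |
|---|---|---|---|---|
| 30, 2 | 6.8 ms | 1.4% | 0.4 ms | 0.0% |
| 30, 4 | 7.7 ms | 1.8% | 1.9 ms | 0.1% |
| 80, 2 | 18.0 ms | 9.7% | 1.0 ms | 0.0% |
| 80, 4 | 20.6 ms | 12.4% | 4.9 ms | 0.8% |

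For the largest case, √(40² + 20.6²) = 45.0 ms, against 40 ms. At 60 bpm the same grid gives 1.3% to 12.1% for the first 1000 and at most 2.4% for the last 1000. With D = 0 there is no difference.

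A separate simulation with other assumptions (heart rate settling by 3 to 10 bpm, τ of 1 to 4 minutes, beat noise SD 30 ms) gave SDNN about 2% to 34% larger with the first 1000 than with the last 1000, and RMSSD unchanged at about 42 ms.

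**3. Other indices.** SD2² = 2·SDNN² − SD1², so SD2 rises with SDNN and SD1/SD2 falls. The trend's root-mean-square beat-to-beat step is at most about 0.16 ms, negligible for RMSSD, pNN50 and SD1. A drift over minutes lies far below the 0.04 Hz lower edge of the LF band. Adding it to simulated 1/f series left LF and HF power unchanged (0.00%, with a Hann taper and mean removal assumed) and moved DFA α2 by at most 0.006.

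**4. Length mismatch.** In simulated 1/f series (exponents 0.8 to 1.0, assumed), SDNN from 256 intervals is about 5% to 10% lower than from 1000 with no treatment effect. This acts in the same direction as the settling trend: roughly 0.95/1.014 = 0.94 to 0.90/1.124 = 0.80, an apparent fall of about 6% to 20%.

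**5. Equal-length alternative.** In the last 256 rest intervals the trend SD is at most 0.3 ms in every case above, so the inflation is nil to two decimals of a percent.

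**The case against.** The case for leaving the rule alone is that it is prespecified and reproducible, and covers most of the rest period. The recording start is inferred, the participant has already lain at rest for 10 minutes, and the settling is assumed throughout. All of that stands, and it limits the point to a risk of unknown size. The supine rest does not remove the later change to sitting, however, and the rule as written gives no protection if settling occurs.

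Four stronger readings are tempting, and the document does not support them:

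- **The last minutes are known to be steadier.** Nothing in the Protocol shows this.
- **The baseline invalidates the spectral or fractal analysis.** Step 3 shows otherwise, and the Protocol itself describes DFA as suited to non-stationary series.
- **The trial's treatment contrast is biased.** The same rule applies in active and sham sessions, so a common settling shift largely cancels.
- **The MS-versus-healthy comparison is biased because the window length depends on heart rate.** With equal settling, the inflation hardly varies with heart rate (12.1% at 60 bpm, 12.4% at 70 bpm). A bias would need settling itself to differ between the groups, and the Protocol gives no figure for that.

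It is also fair to object that changing first to last does not by itself repair the rest-to-needling comparison, since the length mismatch remains. That is accepted, and the fix covers it. Data Analysis speaks only of intra- and intergroup differences, so the rest-to-needling comparison rests on the objective in the Introduction.

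**Conclusion.** The point holds as a minor one, with low confidence in its size. The Protocol fixes a window at the start of the seated rest and sets no settling time aside. If recording starts on sitting down and RR settles by 30 to 80 ms with a time constant of 2 to 4 minutes, a resting SDNN of 40 ms is inflated by about 1% to 12%, against under 1% with the last 1000 beats at 70 bpm and at most 2.4% at 60 bpm. The risk is confined to the rest-to-needling change in SDNN, SD2 and SD1/SD2. The 1000-versus-256 mismatch distorts that SDNN change by a similar amount (about 5% to 10%) and does not depend on any settling.

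**What to change.** - State when the rest recording starts. Replace the first 1000 by the last 1000 clean intervals of the 20-minute rest period, using all available intervals where fewer than 1000 clean ones remain (near 50 bpm).
- For the rest-to-needling change in SDNN, SD2 and SD1/SD2, use segments of equal length, for example the last 256 rest intervals against 256 needling intervals, and say which 256 needling intervals are used.
- Reconcile the Intervention text and Table 2 (needling directly after monitor placement) with the 20-minute seated rest under Analysis of Heart Rate Variability, so that it is clear which recording the rule applies to.

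The cost is a few words in the processing rule. No extra recording is needed, and participants with at least 1000 clean intervals keep the same number of resting beats. The downside is that the window lies closer to needle insertion, so anticipation may enter it; this should be acknowledged.

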HRV analysis will be performed using linear methods (time and frequency domains) and non-linear methods that will be analyzed using the softwares: HRV analysis, CDA_Pro.

Linear Methods (Time and Frequency domain)

In the time domain, the RMSSD, pNN50 and SDNN indexes will be used. The RMSSD which is Square root of the mean of squared differences between successive beat intervals (Marães et al., 2003; Batista et al., 2019). The pNN50 index, in turn, is a sensitive and easily interpretable marker

of the parasympathetic SNA modulation, defined as the percentage of successive differences in the R-R interval whose absolute value exceeds 50ms. SDNN, on the other hand, reflects the participation of both branches of the SNA and corresponds to the standard-deviation of the average of all normal RR intervals, expressed in ms (Pumprla et al., 2002; Aubert et al., 2003; Bittencourt et al., 2005; Ribeiro e Moraes Filho, 2005).

For the analysis of HRV in the frequency domain, low frequency spectral components (LF – range between 0.04 to 0.15 Hertz) will be used in absolute units and high Frequency (HF – range from 0.15 to 0.4Hertz), in normalized units, and the ration between these components (LF/HF), which represents the relative value of each spectral component in relation to the total power, minus the exceptionally low frequency components (VLF). The algorithm used for the spectral analysis will be the fast Fourier transform - FFT (256 s window with 50% overlap) (Vanderlei et al., 2009; Martinelli et al., 2020; Carvalho, 2009).

Nonlinear Methods (Fluctuation Analysis, Depuration of Trends and Poincaré Graph)

For HRV analysis using nonlinear methods, the DFA quantifies the presence or absence of fractal correlation properties of RR intervals and has been validated by time series data. This method calculates the fluctuation of the mean square root of the integral and depurates the time series, allowing the detection of intrinsic self-similarity embedded in the non-stationary time series. The DFA graph is not strictly linear, but consists of two distinct regions of distinct curves, separated at one point, suggesting that there is a short-term fractal scale exponent (a1) during periods of 4-11 beats (or 4 to 13), and a long-term exponent (a2), for longer periods (greater than 11 beats) (Carvalho et al, 2009; Moraes et al., 2019; Godoy et al., 2007).

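### The single 256-second FFT window does not fit the 256-interval record at any heart rate above 60 bpm, so the stated spectral rule cannot be carried out on that record

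*Protocol*

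**What the plan says.** Under Linear Methods (Time and Frequency domain), the protocol names one algorithm for LF, HF and LF/HF: "fast Fourier transform - FFT (256 s window with 50% overlap". It gives no second window, no zero-padding rule and no separate setting for short recordings. The lowest frequency of interest comes from the LF band ("LF – range between 0.04 to 0.15 Hertz").

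Under Analysis of Heart Rate Variability, record length is set in beats and differs by state. For rest: "analysis of HRV data in the sitting position, 1000 consecutive RR intervals will be used". For the other state: "during the tasks, 256 consecutive intervals will be used". Ectopic beats and artifacts are removed, and "there will be no substitution, only the elimination of artifacts". Then: "After manual filtering, the first 1000 beating intervals are chosen", followed by the condition that "only series with more than 95% of sinus beats will be included in the study". The protocol does not say whether that last choice of 1000 intervals applies only to rest or also to the tasks.

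The Intervention section sets needling at 20 minutes, and the HRV section sets seated rest at 20 minutes. HRV is listed as the primary outcome in Table 2, and the Introduction states the aim of studying autonomic behaviour before, during and after therapy.

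**The concern.** A window in seconds and a record in beats agree only at exactly 60 bpm. Above that rate the 256-interval record is shorter than the window meant to be laid over it, and the 50% overlap has nothing to overlap. The analyst or the software must then shorten or pad the window in a way the protocol does not state.

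The resting record is almost four times as long and takes several windows. The two states would then be measured by different estimators: an average over several segments at rest, and one shortened segment during needling. A within-person comparison of LF, HF and LF/HF from before to during needling would mix any physiological change with a change of estimator, and the needling values would be much noisier. HRV is the primary outcome, so the setting needs to be one that can be executed.

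**Working it through.** **Inputs from the protocol.** Window 256 s; overlap 50%, so a step of 128 s; 1000 intervals seated; 256 intervals during the tasks; needling 20 minutes; lower LF limit 0.04 Hz.

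**Assumed.** Heart rate, which the protocol does not give; shown for 60 to 100 bpm.

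**Formulas.** Duration T = beats × 60 / heart rate. Full windows = 0 if T < 256 s, otherwise floor((T − 256)/128) + 1.

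| Heart rate (bpm) | 256 intervals (s) | Full windows | 1000 intervals (s) | Full windows |
|---|---|---|---|---|
| 60 | 256.0 | 1 | 1000.0 | 6 |
| 65 | 236.3 | 0 | 923.1 | 6 |
| 70 | 219.4 | 0 | 857.1 | 5 |
| 75 | 204.8 | 0 | 800.0 | 5 |
| 80 | 192.0 | 0 | 750.0 | 4 |
| 90 | 170.7 | 0 | 666.7 | 4 |
| 100 | 153.6 | 0 | 600.0 | 3 |

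**Break-even points.** One window needs 256 × 60 / HR ≥ 256, so HR ≤ 60 bpm. Two windows at 50% overlap need 256 + 128 = 384 s, so HR ≤ 256 × 60 / 384 = 40 bpm. Between these rates exactly one window fits and the overlap still cannot operate.

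**Is there enough recording?** In 20 minutes, beats = 20 × HR: 1400 at 70 bpm, 1600 at 80, 1800 at 90. One full window needs 256 × HR / 60 beats: 299, 342 and 384 (rounded up). Two windows need 448, 512 and 576. The recording is long enough; the conflict comes only from the 256-interval rule.

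**Effect on precision.** A simulation with no true change used an assumed spectrum (LF peak at 0.10 Hz, HF peak at 0.25 Hz, 1/f power below LF, Hann window, 75 bpm):

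- CV of LF power was about 15% for 1000 intervals with 256 s windows, and about 36% for 256 intervals with one shortened window. Other assumed spectra gave 13% to 14% and 31% to 38%.
- With windows of 64 to 100 s on the same 256 intervals, the CV was still 29% to 31%. Shortening the window removes (36 − 31)/(36 − 15) = 24% to (36 − 29)/(36 − 15) = 33% of the excess. The rest is due to record length. As a rough check, scaling by the square root of the length gives 15% × √(1000/256) = 15% × 1.98 = 30%.
- SD of log LF/HF was about 0.20 at rest and 0.47 with the shortened window.
- Mean raw LF/HF rose by about 7% (6% to 10% over 65 to 90 bpm) with no true change. The median moved by at most about 3%, so the rise is mainly skewness of a ratio.

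**The case against.** **The 1000-interval sentence may govern.** The protocol says "After manual filtering, the first 1000 beating intervals are chosen" without limiting this to rest. If it covers needling, the window fits at every plausible heart rate and the problem disappears. This stands as a condition on the point. It would, however, contradict the explicit 256-interval rule, so the text needs reconciling either way. For the same reason a reader should not infer that the window is at fault whatever record is used.

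**Tasks may not mean needling.** The reading is an inference. It is the natural one: the sentence just before speaks of analysis during acupuncture, and the HRV section describes no other task.

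**LF and HF can still be computed.** This is correct. At 75 bpm, 204.8 s holds 204.8 × 0.04 = 8.2 cycles at the lower LF limit, so a shorter or padded window would give values. A reader might infer that the indexes cannot be obtained at all; the documents support only that they cannot be obtained by the stated rule.

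**Active and sham share the record.** Both needling conditions would use the same length and estimator, so bias in mean raw LF/HF should largely cancel between them. That stands. The extra noise does not cancel, and the before/during comparison keeps both.

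**Most of the noise is not the window's doing.** This also stands: roughly two thirds to three quarters of the excess CV comes from using 256 intervals instead of 1000. A shorter window alone is therefore a weak remedy.

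**Conclusion.** The point holds as an internal mismatch: on the reading that 256 intervals govern needling, the stated FFT rule cannot be applied to that record above 60 bpm, and its overlap cannot operate above 40 bpm. At 60 to 100 bpm the resting record holds 3 to 6 full windows and the needling record at most one. The arithmetic is exact; only the heart rates are assumed. The loss of precision, a CV of LF power of about 15% against 36% at 75 bpm, depends on the assumed spectrum and is mostly an effect of record length. It should be corrected, and correction is cheap.

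Two wider inferences are not supported. A reader might suppose that the study hypothesis rests on the frequency-domain indexes. The Introduction names no index, and the methods also link pNN50, SDNN and the Poincaré measures to autonomic modulation; none of these uses the window. A reader might also extend the criticism to "a long-term exponent (a2), for longer periods (greater than 11 beats". The protocol sets no upper box size for it, so any figure would rest on an assumed cap, and nothing there is stated wrongly.

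**What to change.** In Analysis of Heart Rate Variability, state one record length for rest and needling, long enough to hold several overlapping windows, and say explicitly whether the 256-interval rule or the first-1000 rule applies to needling. The simplest choice is 1000 intervals in both states with the 256 s window kept. Both recordings last 20 minutes, which yields 1000 beats at 1000/20 = 50 bpm or faster, so a rule is needed for slower rates. Equal beats still give slightly unequal window counts if heart rate shifts (5 at 75 bpm, 4 at 80); fixing the length in seconds would remove that.

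If 256 intervals must be kept, change the setting under Linear Methods to one shorter window that fits the shortest record and cut the resting record to the same length. A 64 s window with 50% overlap, for example, gives floor((153.6 − 64)/32) + 1 = 3 segments even at 100 bpm and holds 64 × 0.04 = 2.6 cycles at the lower LF limit. The price is coarser frequency resolution and a noisier resting estimate, with needling noise little improved.

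Either way the cost is a sentence or two and a software setting. No new data are required.

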Besides that, neuromodulation with acupuncture can provide vital information about the functional organization of the nervous system (Ulloa, Quiroz-Gonzalez and Torres-Rosas, 2017). In this way Quispe-Cabanillas et al., (2012) evaluated thirty-one patients with Relapsing-Remitting Multiple Sclerosis undergoing treatment with immunomodulators, and they conclude that Electroacupuncture improved various aspects of quality of life, including a reduction in pain and depression. In addition, according to Anderson et al., (2014), evaluate the ability of acupuncture to modulate HRV could imply that acupuncture may function by regulating and integrating the various physiological systems in the body. In their review all randomized placebo-controlled trials (a total of 16) suggest that acupuncture improves HRV, but 12 of these studied healthy subjects, four studied subjects with medically diagnosed conditions, and none of these have studied these effects in people with MS.

Given the above, the Objective of this study is to evaluate the heart rate variability in individuals with MS during the applicability of Acupuncture, to analyze the behavior of the autonomic nervous system before, during, and after therapy and the changes of the condition. It is necessary to emphasize the need for studies that prove the benefits of the adopted procedures, to be better understood and consequently better applied, expecting better results, and assisting rehabilitation professionals in choosing the therapeutic program based on scientific evidence. Considering the deliberations presented, as a hypothesis, we believe that individuals with MS will present greater sympathetic modulation that will tend to balance during and after the applicability of Acupuncture.

2. Methods

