INTERVENTIONS	
For data collection, the following instrument will be used: Visual Analogue Scale of Pain. This scale will be applied at the beginning of each intervention day. In sequence, the participants will perform the Thermography protocol, which comprises capturing images in various postures in the orthostatic position (in the initial and final assessments).
 
Afterwards, the participants will remain in the supine dorsal position on a stretcher at rest for 10 minutes to start the SNA analysis with the Ryodoraku (device that measures the electroconductivity of certain points on the skin) by the digital reading of the 24 points called ryodos (SCILIPOTI, 2007).
 
Continuing the procedure, immediately after the placement of the Polar V800, an instrument for analyzing HRV, the placing of needles at the points carefully selected for this research begins. The needling will proceed for the experimental group using specific Traditional Chinese Acupuncture points: E36, BP6, F3, IG4, for 20 minutes while the control group will receive needling in sham points (points not recognized as Acupuncture points), with the duration of 20 minutes.
 
Final phase, new reading with Ryodoraku and Thermography.

KEY INCLUSION AND EXCLUSION CRITERIA	
Inclusion Criteria
 
This study will include individuals diagnosed with MS, aged over 18 years, with motor and intellectual capacity to understand the evaluations, with light and moderate functional classification levels (EDSS scale) and who accept to participate in the study through agreement with informed consent form.
 
Exclusion Criteria
 
Participants will be excluded if they (1) do not understand the evaluations; (2) cardiac diseases that impede the assessment of HRV; (3) have a cardiac pacemaker.

STUDY TYPE INTERVENTIONAL ALLOCATION:	Randomized
MASKING:	Double-blind
ASSIGNMENT:	Crossover
PRIMARY PURPOSE:	Treatment

DATE OF FIRST ENROLMENT	September 2021
TARGET SAMPLE SIZE	80 participants
RECRUITMENT STATUS	Recruiting
PRIMARY OUTCOME(S)	Heart Rate Variability improvement
KEY SECONDARY OUTCOME(S)	Ryodoraku and Thermography improvement

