The Poincaré graph is a quantitative method of analysis, based on the changes in the sympathetic or parasympathetic modulation of the heart rate over the subsequent intervals, without the need for the property of data stationarity (Godoy et al., 2007; Guerra et al., 2019). The following indexes will be calculated: SD1 (standard deviation of instantaneous beat-to-beat variability in the short term), SD2 (long-term standard deviations of continuous R-R intervals) and the SD1/SD2 ratio (BRUNETTO et al., 2005).

Primary Outcome

We will observe changes in the ANSs after intervention with active acupuncture and sham acupuncture in patients with MS, during a period of 28 days and after 2-weeks follow-up, following by more 28 days of intervention.

Secondary Outcome

We will analyze changes in Ryodoraku and Thermography regarding both interventions (active and sham acupuncture).

DATA ANALYSIS

If the data meet the assumptions for using parametric analysis, analysis of variance (ANOVA) will be performed to identify intra and intergroup differences. The differences, if any, will be detected by Bonferroni's post-hoc test. If the assumptions of ANOVA are not met, non-parametric analyses will be used to identify and locate the differences: Friedman -post-hoc Wilcoxon as test (intra-group) and Kruskal-Wallis and U of Mann-Whitney as post-hoc test (intergroups). A significant level of 0,05 (5%) will be defined and all intervals built along the work will be with e 95% statistical confidence. The statistical program will be the SPSS (Statistical Package for Social Sciences), version 11.0 (Frankfort-Nachmias and Leon-Guerrero, 2005).

RISKS AND BENEFITS

The research is based on analyzing the variability of SNA – Autonomous Nervous System with the therapeutic use of an Acupuncture protocol and a complementary protocol of Thermography in individuals with Multiple Sclerosis. Therefore, it is considered research with human beings and as such has the duty to safeguard the integrity of those involved. This safeguard will be in relation to the questions of privacy, secrecy, and the minimization of any discomfort.

Risks

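### The primary outcome names no HRV index: eleven unranked indices share one 5% level, and the sample size rests on a motor score the trial does not schedule

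*Protocol*

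**What the plan says.** **Primary outcome.** The Primary Outcome paragraph reads "We will observe changes in the ANSs after intervention with active acupuncture and sham acupuncture in patients with MS", over two 28-day blocks separated by two weeks. Table 2 gives "Heart Rate Variability improvement". The hypothesis closing the Introduction adds a direction, expecting "greater sympathetic modulation that will tend to balance during and after the applicability of Acupuncture", but selects no index.

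**Indices.** Under Linear Methods, "the RMSSD, pNN50 and SDNN indexes will be used" in the time domain, with LF, HF and LF/HF in the frequency domain. Under Nonlinear Methods come the exponents a1 and a2 and then the Poincaré set, "The following indexes will be calculated: SD1", followed by SD2 and SD1/SD2. No index is placed above another.

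**State and visit.** Analysis of Heart Rate Variability says that for the sitting position "1000 consecutive RR intervals will be used, and during the tasks, 256 consecutive intervals will be used". Table 1 marks HRV throughout the schedule.

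**Testing.** In Data Analysis, ANOVA "will be performed to identify intra and intergroup differences", with Bonferroni as its post-hoc test. If assumptions fail, rank tests are used and no correction is named. "A significant level of 0,05 (5%) will be defined", once, for everything.

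**Sample size.** Section 2.1 bases the calculation on a main outcome that it calls a motor score, with an effect size of 0.65 from a study in another condition and treatment. Table 1 contains no motor score.

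**The concern.** A primary outcome has to be a variable that two analysts would compute in the same way. Here they could reasonably choose RMSSD, LF/HF, a1 or SD1/SD2, and each could call the choice HRV improvement. For ratios and fractal exponents, improvement does not even fix a direction. The one place that names a specific main outcome, the sample-size text, names something this trial does not schedule, so it cannot settle the question.

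At stake is the meaning of the 5% level. It holds for a claim resting on one test fixed in advance. It does not hold for the best of several indices chosen after the results are known. The multiplicity method may be left to an SAP, but the identity of the primary variable is protocol content, and this protocol does address it, in two vague forms and one conflicting one.

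**Working it through.** **1. Count of indices.** Time domain 3 (RMSSD, pNN50, SDNN), frequency domain 3 (LF, HF, LF/HF), fractal exponents 2 (a1, a2), Poincaré 3 (SD1, SD2, SD1/SD2): 3 + 3 + 2 + 3 = 11.

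**2. The plan's own sample size.** Inputs from section 2.1: d = 0.65, alpha 0.05, power 0.80; stated result 30 in total, 15 per group. Sidedness is not stated.
- Two independent groups, two-sided: n = 2(1.960 + 0.842)² / 0.65² = 37.2, so 38 per group (39 by the t distribution).
- Two independent groups, one-sided: 2(1.645 + 0.842)² / 0.65² = 29.3, so 30 per group, or 60 in total.
- Paired: 21 two-sided, 17 one-sided.

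None of these gives 30 in total; 30 matches only the one-sided figure per group. This is a side finding on which the main point does not depend, but it bears on restating the calculation.

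**3. What the stated correction covers.** Bonferroni follows an ANOVA, and an ANOVA is run on one index. The correction therefore applies to pairwise comparisons within an index, not to the choice among indices. On the rank-test route no correction is named.

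**4. Chance of at least one false positive across indices.** Assumption: each index is tested two-sided at 5%. With k independent tests it is 1 − 0.95^k, so 1 − 0.95^11 = 43.1% and 1 − 0.95^7 = 30.2%. HRV indices are related, so these are upper illustrations. With k equally correlated normal statistics (400,000 draws, rejecting when any absolute value exceeds 1.96):

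| Assumed correlation | 0.3 | 0.5 | 0.7 | 0.9 |
|---|---|---|---|---|
| 11 indices | 37% | 30% | 22% | 13% |
| 7 indices | 27% | 23% | 18% | 11% |

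Seven is a cautious count: 11 less SD1 (which tracks RMSSD), SD2 and SD1/SD2 (which derive from RMSSD and SDNN), and one of normalized HF and LF/HF. That last merger is exact only for rank tests. Under t-tests or ANOVA the two are different tests, and at least one rejects about 7% of the time under the null.

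**5. Power with a single primary test.** Assume SD 1 in each condition and correlation 0.5 between conditions. The SD of the within-person difference is then √(2 × (1 − 0.5)) = 1. Power comes from the noncentral t with noncentrality d√n and n − 2 degrees of freedom. Completers: 40, or 40 × 0.8 = 32 after the stated 20% withdrawal.
- d = 0.65: noncentrality 4.11 and 3.68, power 98% and 94%.
- d = 0.65 with all eleven indices kept as primary, each at 0.05/11 = 0.0045: power 85% and 72% by the same formula.
- d = 0.3 (assumed): noncentrality 1.90 and 1.70, power 46% and 38%.

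**The case against.** The strongest reply is that the design already identifies what is being tested. Section 2.1 declares a randomized sham-controlled crossover, and both outcome paragraphs name active and sham acupuncture. That stands. A reader might infer that active versus sham in MS participants is not the intended comparison at all, but the documents do not support this. What remains is wording: *group* means healthy or MS in section 2.1, sham or active in Table 2 and Intervention, and also the sequences A-S and S-A, so an intergroup test could be misread as MS versus healthy.

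A reader might also infer that every state and visit adds another uncorrected test. The text does not say so. Visits within one index can be levels of a repeated factor, with Bonferroni applied to their pairwise comparisons, and recording states can enter in the same way. Figures that multiply indices by states are therefore left out. The gap across indices stays open, as does the rank-test route.

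The period term and the exact test can properly wait for an SAP. Nor can one say that an unpaired analysis would merely be conservative. Pooling the sessions in each condition as if independent could inflate the error instead: about 14% under assumed correlations of 0.8 within and 0.5 between periods.

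Finally, the wording about observing changes can be read as mechanistic. Table 2, however, gives treatment as the primary purpose, and the plan sets a significance level.

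**Conclusion.** The point holds and should be settled before analysis. The protocol has no identifiable primary variable, and its single 5% level does not protect a primary claim drawn from the listed indices. The false-positive risk of such a claim is roughly 11% to 37%. That range spans seven to eleven indices and assumed correlations from 0.9 to 0.3, and it takes each index as tested two-sided at 5%. It illustrates the problem and does not measure this trial's error rate. The 43% for eleven independent tests should not be quoted as the actual risk, because these indices are related by construction. Even the most cautious case is more than twice the stated level. Confidence is high on the missing designation and on the conflict with the motor score. The *group* labels are a wording matter and do not carry the rating.

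**What to change.** Before any outcome data are seen by allocation:

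1. Designate one HRV index, with its recording state and one visit or summary, as the single primary outcome for active minus sham within MS participants. The choice is the sponsor's and should fit the hypothesis in the Introduction and the Primary Outcome paragraph. Use the same wording in Table 2.
2. Make the other indices secondary or exploratory.
3. In section 2.1, replace the motor score with that outcome and restate the basis of the sample size, including the effect size, sidedness and paired structure.
4. Use *group* consistently in section 2.1, Table 2, Intervention and Data Analysis.

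None of this adds visits or procedures. The price is that primary success can no longer be claimed on the other indices; in return, the full 5% stays with one test. The restated sample size may be less comfortable than it now looks. The 98% and 94% power figures borrow an effect size from a motor score, and an assumed d of 0.3 would leave 46% and 38%.
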